5.3 STRATEGIES FOR RECRUITMENT AND RETENTION

Hospital Discharge Study

Eligible pharmacists will be selected by the pharmacy managers at each site. Eligibility includes training in transitions of care and/or post-discharge care.

A daily Epic report will be generated at each site to identify eligible patients. A research assistant will conduct a brief chart review to confirm eligibility before randomizing the patient using REDCap. For quality assurance, operational reports will be obtained from the emergency department and cross-checked with the EIS report to ensure all patients who may be eligible for the study are accurately identified. The study coordinator will stop randomizing patients if the number of patients concurrently receiving the intervention on any given weekday exceeds the workload capacity of pharmacists at each site. Study coordinators will communicate with pharmacists to regularly re-assess the maximum threshold of concurrent patients in the intervention arm. This strategy aims to reduce the potential for pharmacist burnout and to optimize intervention quality.

Once the patient has been randomized to the intervention or control arm, the clinical pharmacist will approach the patients in the intervention arm.

Focus Group/Interviews Study

We will use a purposive sampling design by role and department to determine eligibility. Eligible participants will receive an email from study staff inviting them to participate in the focus groups, and/or interviews. To enhance recruitment, we will offer a \$125 honorarium to nurses and a \$250 honorarium to physicians for their participation in a 60-90 minute focus group or interview.

Time and Motion Study

Pharmacists will be approached for oral consent at the beginning of a clinic day or clinical shift. Potential participants will be approached, given an information sheet, and the nature of the study will be explained. Inclusion Criteria: Pharmacists participating in the PHARM-DC intervention actively seeing patients and responsible for generating the majority of documentation for the clinical visit.

6 STUDY INTERVENTION

6.1 STUDY INTERVENTION(S) ADMINISTRATION

6.1.1 STUDY INTERVENTION DESCRIPTION

PHARM-DC Intervention Overview

Pharmacists at both study sites have experience in providing discharge counseling and in making post-discharge phone calls. This experience will ensure that PHARM-DC is being tested in its best light. The Toolkit content and 1-2 hours of introductory training add three major components:

1. Rather than incorporating content based solely upon their prior training and experience, pharmacists will use the *PHARM-DC Toolkit*, which *summarizes the evidence* for post-discharge medication management.
2. Pharmacists will *assess patient needs* and *customize accordingly*. All patients will receive one discharge counseling visit and one post-discharge phone call, but pharmacists will find that some patients need further phone calls, interventions, referrals, or other interactions.
3. Although pharmacists have long been successful in leading med rec interventions, most work focused on *what medications patients had been prescribed and are taking*. This is a necessary step, but we believe most benefit occurs from the subsequent step of figuring out what medications patients *should be taking*.

PHARM-DC toolkit:

- 1) Pharmacist review of discharge med rec and medication appropriateness (e.g., reduction in polypharmacy);
- 2) In-hospital room visit to screen for previous barriers to safe medication use, initiate management of these barriers, and communicate with post-discharge providers regarding likely actions that will need to be taken;
- 3) Post-discharge phone call by a pharmacist 1-3 days after discharge to screen for patient/caregiver lack of understanding of their medication regimen, medication non-adherence, early side-effects, lack of knowledge of what ADEs to watch for and what to do if they occur, other barriers to safe medication use, and management of these problems;

4) Based on this risk assessment, pharmacists will tailor the interventions to each patient. The personalized intervention may include:

- a. **Patient education, counseling, and coaching** regarding the importance of taking medication as prescribed and contacting a designated caregiver or provider if there are problems;
- b. **Taking further steps to improve medication appropriateness;**
- c. **Post-discharge assistance with obtaining medications**, including drug assistance programs (for reduced pricing) and linkage with community or social service organizations;
- d. **Pharmacist communication with key inpatient and outpatient providers** (e.g., PCPs; skilled nursing facilities; inpatient rehabilitation hospitals, including the California Rehabilitation Institute) to ensure that they understand changes to their patient's discharge medication regimen, including why those changes were made and recommended actions to take. This includes requesting Medication Administration Records (MAR) from downstream providers to facilitate this type of communication;
- e. **Communication with each patient's pharmacy** to ensure the pharmacy has an updated medication list, with focus on newly discontinued medications, and to encourage patient education as needed when patients fill their prescriptions;
- f. **Use of illustrated pill cards, pillboxes (traditional and electronic), and other tools** to help patients with low literacy better understand and adhere to their medication regimens;
- g. **Health information technology such as patient portals and texting** chatbots to facilitate communication between patients, pharmacists, and other providers after discharge;
- h. **Home pharmacist visits for high-risk patients** to educate them and to identify and manage challenges to safe medication use.

6.2 MEASURES TO MINIMIZE BIAS: RANDOMIZATION AND BLINDING

Randomization will be performed via the REDCap (Research Electronic Data Capture) system. REDCap is a secure, web-based application supporting data capture for research studies, providing:

- 1) an intuitive interface for validated data entry;
- 2) audit trails for tracking data manipulation and export procedures;
- 3) automated export procedures for seamless data downloads to common statistical packages; and;
- 4) procedures for importing data from external sources.

REDCap will incorporate allocation tables generated in R. Study participants will be randomized 1:1 to the two arms of the study and stratified by site. Arm assignment will not be actively masked, but most clinical personnel and patients will remain unaware of the trial, just as they are unaware of the details of most post-discharge medication management practices currently.

6.3 STUDY INTERVENTION COMPLIANCE

We will use EHR documentation to assess study intervention compliance. This will include detailed reports generated from Epic about pharmacist documentation notes and phone calls.

7 STUDY INTERVENTION DISCONTINUATION AND PARTICIPANT DISCONTINUATION/WITHDRAWAL

7.1 LOST TO FOLLOW-UP

Hospital Discharge Study

Patients who leave the state or country after their hospital discharge or who do not answer phone calls post-discharge will be considered lost to follow-up and this will be recorded in the CONSORT diagram.

7.2 ADVERSE EVENTS AND SERIOUS ADVERSE EVENTS

7.2.1 DEFINITION OF ADVERSE EVENTS (AE)

Adverse event means any untoward medical occurrence associated with the use of an intervention in humans, whether or not considered intervention-related (21 CFR 312.32 (a)).

7.2.2 DEFINITION OF SERIOUS ADVERSE EVENTS (SAE)

An adverse event (AE) or suspected adverse reaction is considered "serious" if, in the view of either the investigator or sponsor, it results in any of the following outcomes: death, a life-threatening adverse event, inpatient hospitalization or prolongation of existing hospitalization, a persistent or significant incapacity or substantial disruption of the ability to conduct normal life functions, or a congenital anomaly/birth defect. Important medical events that may not result in death, be life-threatening, or require hospitalization may be considered serious when, based upon appropriate medical judgment, they may jeopardize the participant and may require medical or surgical intervention to prevent one of the outcomes listed in this definition.

Examples of such medical events include allergic bronchospasm requiring intensive treatment in an emergency room or at home, blood dyscrasias or convulsions that do not result in inpatient hospitalization, or the development of drug dependency or drug abuse.

7.2.3 CLASSIFICATION OF AN ADVERSE EVENT

7.2.3.1 RELATIONSHIP TO STUDY INTERVENTION

We do not anticipate any adverse events related directly to the study intervention. Therefore, AEs will be classified as:

Not Related – There is not a reasonable possibility that the administration of the study intervention caused the event, there is no temporal relationship between the study intervention and event onset, or an alternate etiology has been established.

Each site PI, [name] (CSMC) and [name] (BWH) will be responsible for determining whether an adverse event (AE) is expected or unexpected. An AE will be considered unexpected if the nature, severity, or frequency of the event is not consistent with the risk information previously described for the study intervention. AEs will be reported to the DSMB for evaluation.

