1.3 SCHEDULE OF ACTIVITIES (SOA)

(1) *Pharmacist-led Hospital Discharge Care Intervention:*

- a. Eligible pharmacists at each study site will be selected to participate in the intervention based on their training in transitions of care.
- b. Using a daily Epic report generated by EIS, a coordinator at each site will identify eligible patients and notify pharmacists. Trial enrollment will occur for eligible patients admitted every day prior from Monday to Friday.
- c. Randomization will be performed via the REDCap (Research Electronic Data Capture) system.
- d. All eligible patients (both arms) will receive the Best Possible Medication History (BPMH)
- e. Patients in the Study arm:
 - i. On hospital day 1, or as soon as possible: Receive an Initial Medication Regimen Assessment. Clinical pharmacists assess regimen appropriateness, assess barriers to medication adherence, start filling out the Actions for Assessing Adherence Barriers worksheet
 - ii. On hospital day 1, or as soon as possible: Receive a Pre-Discharge Intervention, which, depending on the patient condition, might include a: trial to discontinue certain medications during the hospital; discussion of side effects, flags for new medications prescribed, education about critical barriers to adherence.
 - iii. On day of discharge: Receive an At-Discharge Intervention, which may include a brief discussion of medication changes, discussion of side effects, discussion of red flags for new medications. Clinical pharmacists will also consult with inpatient clinicians and pharmacists to discuss the medication list and will ensure that the e-prescribing is done appropriately.
 - iv. 1-3 days after discharge: Receive a Post-Discharge Intervention, which includes a call with a patient to discuss the patient's regimen, discussion of side effects, red flags of new medications, a motivational interview, a discussion of barriers to adherence. Other tasks might include a phone call with the patient's primary care physician.
 - v. After initial phone call: Some patients, depending on need, might receive a second phone call if needed, a video visit, clinic visit with pharmacist, embedded mental health.
 - vi. For any of the above-mentioned activities, patients may be contacted by pharmacists over the phone instead of in-person to reduce COVID-19 exposure to patients, caregivers, and pharmacists.
- f. Patients in the Control arm:

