2.3 RISK/BENEFIT ASSESSMENT

2.3.1 KNOWN POTENTIAL RISKS

Hospital Discharge Study

This is a low-risk intervention. Since the intervention is already being conducted at the two sites by clinical pharmacists when there is administrative capacity to do so, we do not anticipate any additional risks involved with the hospital discharge intervention.

There is a small risk of breach of confidentiality with regards to the electronic health records data collected by the researchers at the end of the study; however, all data will be kept on password-protected, encrypted study site computers. Only investigators and study staff who are IRB-approved will have access to the study data. Since we are examining data at the end of the intervention, the data analysis is similar to a retrospective secondary data analysis.

To reduce the risk of COVID-19 exposure, some or all of the intervention activities (medication reconciliation, patient/caregiver education and counseling) will be conducted over the phone.

Focus Groups and Interviews

Individuals who participate in the focus groups and/or interviews may experience mild discomfort about certain questions. However, they will be reminded at the beginning of the focus group that they are not required to answer any questions they find cause discomfort and that they may stop the focus group/interview at any time.

There is also a small risk of breach of confidentiality. Interviewees/participants of focus groups/interviews will be given number identifiers, which will be kept separate from their identifiers/demographic information. Only the study staff will have access to the identifiers. This sub-study will not include any patient observation or use of PHI.

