7.2.4 TIME PERIOD AND FREQUENCY FOR EVENT ASSESSMENT AND FOLLOW-UP

The occurrence of an adverse event (AE) or serious adverse event (SAE) may come to the attention of study personnel during study visits and interviews of a study participant presenting for medical care, or upon review by a study monitor. Study staff will immediately notify the principal investigator ([name]) upon becoming aware of deaths occurring in study participants. The PI will report deaths to the NIA PO within 48 hours by email and submitting the appropriate case report form (CRF).

Deaths and same-hospital readmissions (inpatient, observation, or emergency department visits) occurring within 90-days of hospital discharge will be collected retrospectively from the patient's medical record every six months through the study. All AEs/SAEs will be reported in a semi-annual summary safety report to the Data Safety Monitoring Board (see Section 9.1.4).

All AEs including local and systemic reactions not meeting the criteria for SAEs will be captured on the appropriate CRF. Information to be collected includes event description, time of onset, clinician's assessment of severity, relationship to study product (assessed only by those with the training and authority to make a diagnosis), and time of resolution/stabilization of the event. All AEs occurring while on study must be documented appropriately regardless of relationship. All AEs will be followed to adequate resolution.

Any medical condition that is present at the time that the participant is screened will be considered as baseline and not reported as an AE. However, if the study participant's condition deteriorates at any time during the study, it will be recorded as an AE.

Changes in the severity of an AE will be documented to allow an assessment of the duration of the event at each level of severity to be performed. AEs characterized as intermittent require documentation of onset and duration of each episode.

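### Section 7.2.3.1 defines only a Not Related causality category, so the protocol's scheme has no place for an adverse event that fails that definition

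*Combined protocol and SAP*

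**What the plan says.** Section 7.2.3.1 opens with "We do not anticipate any adverse events related directly to the study intervention. Therefore, AEs will be classified as" and gives a single entry: "Not Related – There is not a reasonable possibility that the administration of the study intervention caused the event". Two alternative grounds follow in the same definition: no link in time, or another cause already established. The section then moves to a different judgement. Each site PI "will be responsible for determining whether an adverse event (AE) is expected or unexpected", and events are passed to the DSMB.

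The neighbouring sections treat cause as an open question. Section 7.2.1 states: "Adverse event means any untoward medical occurrence associated with the use of an intervention in humans, whether or not considered intervention-related". Section 7.2.4 lists among the items to be collected "relationship to study product (assessed only by those with the training and authority to make a diagnosis" (the parenthesis closes there in the source), and adds: "All AEs occurring while on study must be documented appropriately regardless of relationship".

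The premise behind the single category appears in section 2.3.1, where the authors write that "we do not anticipate any additional risks involved with the hospital discharge intervention". Section 1.3, however, lists among the possible pre-discharge activities in the study arm a "trial to discontinue certain medications during the hospital".

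**The concern.** Expecting no related events is a reasonable prior for a low-risk service. It is not a reason to define only the answer that agrees with it. Section 7.2.3.1 moves from the one to the other in two sentences.

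What is at stake is the meaning of the causality data. If staff follow 7.2.3.1, a statement that no adverse event was related to the intervention carries no information, because no other result could have been recorded. This matters here for two reasons. The intervention can lead to changes in a patient's medicines, so a related event is conceivable on the protocol's own description. And section 9.1.1 rests the waiver of consent partly on minimal risk, a premise that causality assessment should be able to test.

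**Working it through.** No sample size, error rate or effect size enters this point, and the plan gives no figure to reproduce. The check is textual.

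**1. Count the categories.** Causality categories defined in 7.2.3.1: one (Not Related). Categories defined there or elsewhere in the documents that would hold a related event: none. The omission does not look accidental, since the section states its reason for the single entry and then continues intact into expectedness.

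**2. Test whether the one category covers every event.** The definition offers three grounds joined by *or*:
- A: no reasonable chance that the intervention was the cause;
- B: no link in time;
- C: another cause established.

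An event is Not Related if A or B or C holds. Each ground can hold or fail, which gives 2 × 2 × 2 = 8 combinations. Seven satisfy at least one ground. The eighth (a reasonable chance of causation, a link in time, no other cause established) satisfies none and has no category. That is the combination a causality assessment exists to find. These are logical cases, not frequencies, and say nothing about how often the eighth would occur.

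**3. Set the sections side by side.**

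| Section | What it assumes about relationship |
|---|---|
| 7.2.1 | An adverse event may or may not be related |
| 7.2.4 | Relationship is judged by someone qualified to diagnose, and recorded; events are documented whatever the answer |
| 7.2.3.1 | One answer is defined |

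The first two need at least two possible answers. A qualified assessor has nothing to decide if there is only one.

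**4. See whether expectedness fills the gap.** It does not. Expectedness asks whether an event is consistent with the risk information already described; relationship asks whether the intervention caused it. Since 2.3.1 foresees no additional risk from the discharge intervention, a clinical event arising from background illness could be judged unexpected just as readily as one caused by a medication change.

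**5. Is a related event conceivable?** Yes. Section 1.3 allows a trial of stopping certain medicines in hospital, and sections 8.4.5 and 8.4.6 hypothesise that the intervention alters prescribing and reduces fall injuries through medication-related risk factors. If regimen changes can cause benefit, harm by the same route cannot be excluded by definition.

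**The case against.** A reader might infer more: that related harm cannot be recorded at all, that every event reaching the DSMB is labelled unrelated by rule, and that the trial is bound to a wrong safety conclusion. The documents do not support that.

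- The case report form is not among the documents. Section 7.2.4 provides for a relationship field, and the form may offer other options.
- The single category carries conditions. Staff are not clearly told to code an event as Not Related when it meets none of them; the text leaves such an event undefined.
- Nothing says that the safety conclusion will rest on a count of related events. Section 7.2.4 collects deaths and same-hospital return visits to 90 days with no causality filter. All-cause unplanned utilization at 30 days is the primary outcome (8.4.1), and 30-day mortality is a listed secondary outcome (section 3). In a randomized trial, harm serious enough to cause a return visit or death can appear as a difference between arms without individual attribution.
- Adverse events are judged for expectedness and sent to a DSMB that meets at least semiannually and defines its own data elements (9.1.4).
- The physician has the last word on medication changes (9.1.1), and most components are already in use at both sites.

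All of this stands, and it limits the consequence. It does not remove the inconsistency. Milder events that lead to neither death nor a return visit depend on the adverse event record, and that is where the causality gap lies. The physician's final decision does not break the causal path from a pharmacist's recommendation.

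**Conclusion.** The point holds as an internal inconsistency with a practical effect. Section 7.2.3.1 defines one causality category, has none for an event that fails its criteria, and conflicts with 7.2.1 and 7.2.4. Under that scheme, zero related adverse events would be a product of the rule.

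The number of events affected cannot be estimated from the documents. The 4,888 patients per group in section 8.2 is the planned exposure to the intervention, not a count of misclassified events, and no sensitivity figure can be attached to the scheme. The conclusion assumes that staff code from the protocol text; if the form already offers a related option, what remains is a protocol wording error. Sample size and primary analysis are untouched. The change should be made, because it is cheap and the causality data cannot be interpreted without it.

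**What to change.** 1. In 7.2.3.1, add a Related / possibly related category as the exact complement of the existing one: a reasonable possibility of causation, a plausible link in time, and no other cause established. The two categories then cover every event without overlap.
2. State that the qualified assessor described in 7.2.4 chooses between them, keep expectedness as the separate judgement it already is, and align 7.2.3.1 with 7.2.1 and 7.2.4. Check that the form carries both options.
3. As a further suggestion, which 7.2.4 does not itself require, show adverse events by arm in the DSMB report.

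Prospectively, this costs one protocol paragraph and at most one option on the form. The current version (16.0, 8/25/2023) describes enrolment at one site in the past tense (8.4.7), so some events may already have been coded; that is an inference. If so, re-review causality where feasible, at modest added cost. Where it is not feasible, do not report zero related adverse events as a finding.
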